#### Secondary IOP-Lowering Interventions to Control IOP

If the subject requires another glaucoma procedure to control their IOP, the subject should continue to be followed according to standard of care until the adverse event resolves or 1 month post-re-intervention, whichever is longer. Following this, the subject should be withdrawn from the study.

Subjects who have a secondary IOP-lowering intervention will be considered treatment failures for the purpose of the endpoint analyses. These subjects will be included in the Safety Endpoint analyses through their withdrawal from the study.

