## **11.2 ANALYSIS POPULATIONS**

The intent-to-treat (ITT) analysis population includes all subjects who are enrolled and treated, regardless of whether or not they have a protocol deviation. The per-protocol analysis population (PP) is a subset of ITT, which includes all subjects who have ab-interno transluminal viscoelastic delivery and trabeculotomy, 12 month IOP (or hypotensive medications washed out IOP if the medications can be washed out) and medication data, and have no clinically significant protocol deviations. It should be noted that the ITT subjects with an uneventful study procedure but with SSIs before the 12-month visit will be included in the PP population even if they do not have the 12-month IOP and medication data. The primary analyses on the primary and secondary endpoint analyses will be carried out on the per-protocol population.

The safety data will be summarized based on the ITT population. The primary and secondary endpoint analyses will also be performed on the ITT population.

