## **11.4 EFFECTIVENESS ENDPOINTS AND ANALYSIS METHODS**

Descriptive statistics on continuous variables will include mean, standard deviation, median, minimum, and maximum. Confidence intervals for change from baseline will be included for selected endpoints. Categorical variables will be summarized using frequency counts and percentages. Exact confidence intervals for point estimates may be provided. Statistical testing will be one-sided with a significance level of 0.025 or two-sided significance level of 0.05 unless specify otherwise. Data listings of individual subject data may be provided.

As described above, the primary analyses of the primary and secondary effectiveness endpoints will be based on the PP population, although the analyses will also be performed on the ITT population. The safety data will be summarized based on the ITT population.

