**11.4.4 OTHER IMPORTANT CLINICAL EFFECTIVENESS OUTCOMES**

The analysis will be based on the PP Population.

For subjects treated with hypotensive medications at Screening Visit, the change in number of hypotensive medications from Screening to 12 Month (before washout if it is needed) will be calculated. For subjects treated with SSIs the change in number of hypotensive medications will be assumed to be 0. The descriptive statistics such as mean, standard deviation, median, minimum, and maximum will be used to summarize the change in number of hypotensive medications used at 12 months from Screening. The 95% confidence interval of the mean change will be calculated based on the t-distribution.

The percent change in unmedicated DIOP from baseline to 12 months will be calculated for each eye in the PP population. For eye treated with SSI, the baseline unmedicated DIOP will be used to impute the 12 month unmedicated IOP (i.e. 0% change). The descriptive statistics such as mean, standard deviation, median, minimum, and maximum will be used to summarize the percent change in unmedicated DIOP at 12 months. The 95% confidence interval of the mean percent change will be calculated based on the t-distribution.

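### The deciding per-protocol set can omit re-intervention failures that followed an eventful procedure and have no 12-month data

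*Combined protocol and SAP*

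**What the plan says.** **Deciding set.** Section 11.2 states: "The primary analyses on the primary and secondary endpoint analyses will be carried out on the per-protocol population". Section 11.4 repeats that "the primary analyses of the primary and secondary effectiveness endpoints will be based on the PP population". The intent-to-treat (ITT) analysis is also performed, but it is not the primary one.

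**Who is in PP.** A treated eye must have had both viscoelastic delivery and trabeculotomy, must have 12-month IOP and medication data, "and have no clinically significant protocol deviations". One waiver of the data requirement follows: "ITT subjects with an uneventful study procedure but with SSIs before the 12-month visit will be included in the PP population", even where the 12-month data are absent. The visible text neither defines *uneventful* nor expands *SSI*.

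**How re-interventions count.** The part of section 9.9 on secondary IOP-lowering interventions says: "Subjects who have a secondary IOP-lowering intervention will be considered treatment failures for the purpose of the endpoint analyses". It sets no condition on how the study procedure went. Such subjects are followed for a limited time, and then: "Following this, the subject should be withdrawn from the study".

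**Scoring of SSI eyes.** The one visible scoring rule is in section 11.4.4, for percent change in unmedicated diurnal IOP. SSI eyes are given their baseline value, so no change. That outcome "will be calculated for each eye in the PP population", so the rule applies only to eyes already admitted to PP.

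**The concern.** Sections 9.9 and 11.2 do not fit together. Section 9.9 makes every IOP-lowering re-intervention a failure and makes missing 12-month data its expected consequence. Section 11.2 then forgives the missing data only when the procedure was uneventful. An eye whose procedure was eventful, which needed an IOP-lowering re-intervention before month 12 and which was withdrawn without 12-month data, is a failure by definition but is not in the set that decides the claim.

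The visible PP criteria do not otherwise exclude an eventful procedure. An eye with an eventful procedure that reaches month 12 with data and without a clinically significant deviation stays in PP and can count as a success. A procedural event can therefore remove an eye because it failed and was withdrawn, while a comparable eye that did well is kept. In a single-arm trial tested against a fixed 40%, no control group offsets this.

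**Working it through.** **1. The plan's own figure.** Inputs from section 11.1: null proportion 0.40, alternative 0.55, one-sided 0.025, power 80%, 91 evaluable eyes.

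- Normal approximation: n0 = [(1.960·√(0.40·0.60) + 0.842·√(0.55·0.45)) / 0.15]² = 84.5.
- With continuity correction: (n0/4)·[1 + √(1 + 2/(n0·0.15))]² = 91.05.

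The stated 91 is reproduced.

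**2. The decision rule.** Section 11.4.1 uses the binomial distribution. At n = 91, P(X ≥ 46 | 0.40) = 0.0266 and P(X ≥ 47 | 0.40) = 0.0161, so success needs 47 of 91. Exact power at 0.55 is P(X ≥ 47 | 91, 0.55) = 77.3%.

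**3. Which eyes are affected.** With an IOP-lowering re-intervention before month 12 and no other ground for exclusion:

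| Procedure | 12-month data | Status in 9.9 | In PP by 11.2 |
|---|---|---|---|
| Uneventful | Absent | Failure | Yes, by the waiver |
| Eventful | Present | Failure | Yes, by the base rule |
| Eventful | Absent | Failure | **No** |

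Only the last row is at issue.

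**4. Can a few eyes change the conclusion?** Exact one-sided p against 0.40:

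- 46/91 = 50.5%, p = 0.0266, fails. Leave out one failure: 46/90 = 51.1%, p = 0.0213, passes.
- 47/91 = 51.6%, p = 0.0161, passes. Restore one failure: 47/92, p = 0.0203, still passes. Restore two: 47/93 = 50.5%, p = 0.0254, fails.
- 50/91 = 54.9% is robust: with eight failures restored, 50/99 gives p = 0.0219.

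**5. Chance of false success.** The number m of omitted failures is not in the documents, so a range is assumed. The true rate among all treated eyes is set at exactly 40%. Two conventions are possible:

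- *91 eyes kept* (m more were treated): the rate among kept eyes is 0.40·(91 + m)/91, tested with 47 of 91.
- *91 eyes treated* (91 − m kept): the rate among kept eyes is 0.40·91/(91 − m), tested with the critical value for 91 − m.

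| m | 91 kept | 91 treated (rule) |
|---|---|---|
| 0 | 1.6% | 1.6% (47/91) |
| 1 | 2.0% | 2.6% (46/90) |
| 2 | 2.4% | 2.6% (46/89) |
| 3 | 3.0% | 4.1% (45/88) |
| 5 | 4.3% | 6.1% (44/86) |

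**6. At the planned effect.** If 91 kept eyes succeed at 55%, restoring m failures raises the required successes to 47 (N = 91 or 92), 48 (N = 93 to 95) or 49 (N = 96 or 97). The chance of success is then 77.3% for m = 0 or 1, 70.5% for m = 2 to 4 and 62.9% for m = 5 or 6. The chance that the omission alone decides the result is 0 for m = 1, 77.3 − 70.5 = 6.8 percentage points for m = 2 to 4, and 77.3 − 62.9 = 14.4 points for m = 5 or 6.

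**The case against.** **The exclusion is inferred.** Section 11.2 never says that eventful-procedure SSI eyes are out, and the waiver reads like a clarifying note. *Uneventful* may only restate the first PP criterion, that both steps of the procedure were performed. Eyes with an incomplete procedure would then leave PP whether they succeeded or failed, and the omission would not be confined to failures. This reading is possible and the text does not rule it out. But the base rule demands 12-month data, so an eye that the waiver does not cover is out by default.

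**Redaction.** Parts of 9.7 (surgical procedure), 10.2 (anticipated events) and 11.4.1 (primary endpoint) are blacked out. They may define an eventful procedure or give the SSI scoring rule. That stands as a limit. A scoring rule alone, however, would not alter the PP membership rule, which is visible.

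**Meaning of SSI.** Section 11.4.3 speaks of IOP-related SSIs, which may mean that SSI is broader than the IOP-lowering interventions of 9.9. The point is therefore confined to the latter.

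**ITT.** A reader might infer that ITT is no firm check either, because the imputations in 11.4.1 are optional and four are listed. The documents do not support that for these eyes: the list covers only subjects without an SSI. ITT contains all treated eyes, and 9.9 scores those with an IOP-lowering re-intervention as failures. What remains is that ITT does not decide the claim.

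**Conclusion.** The point holds as a limited inconsistency that should be corrected. On the visible text, a treated eye with an eventful procedure, an IOP-lowering re-intervention before month 12 and no 12-month data is a failure under 9.9 and absent from the primary denominator under 11.2. Unless *uneventful* only restates that both steps were performed, or is defined in redacted text, the omission favours the device.

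The size depends on a count that the documents do not give. It is zero with no such eyes and small with one or two unless the result is near the boundary. With three to five, false success is 3.0% to 4.3% (91 kept) or 4.1% to 6.1% (91 treated), against 1.6% with none.

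Two stronger readings are not supported. A reader might infer that re-intervention eyes in general drop out of PP; those with an uneventful procedure stay in, and so do those with 12-month data and no significant deviation. A reader might also take three omitted eyes as the point where the 2.5% level is breached. That is so with 91 eyes kept, but with 91 treated it is passed at one, partly because the exact test moves in steps.

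The conclusion assumes that SSI here means the secondary IOP-lowering intervention of 9.9.

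**What to change.** Reconcile 11.2 with 9.9. Delete the condition on an uneventful procedure and state that every eye which received the study procedure and had a secondary IOP-lowering intervention, as meant in 9.9, before the 12-month visit is in the primary analysis set as a failure even without 12-month data. Apply the exclusion for clinically significant deviations in the same way to eyes with and without re-intervention, so that the rule is not tilted against the device either. If *uneventful* was meant only as completion of both steps, or is defined in redacted text, 11.2 and 9.9 should say so.

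The change is wording only and needs no added eyes or visits. It can give a slightly less favourable rate: with two restored failures, 50/91 = 54.9% becomes 50/93 = 53.8%. If the kept eyes succeed at 55%, exact power falls from 77.3% to 70.5% with two to four restored failures. If the planned 55% already counts these eyes as failures, nothing is lost against plan.

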## **11.3 DEMOGRAPHICS AND BASELINE CHARACTERISTICS**

Demographic variables gender, race, ethnicity, and age will be summarized for all enrolled subjects treated with OMNI Surgical System, along with medical history. Descriptive statistical summaries of pre-treatment parameters (min, max, median, mean, standard deviation) will also be provided. The same analyses will be performed for the ITT and PP populations.

## **11.4 EFFECTIVENESS ENDPOINTS AND ANALYSIS METHODS**

Descriptive statistics on continuous variables will include mean, standard deviation, median, minimum, and maximum. Confidence intervals for change from baseline will be included for selected endpoints. Categorical variables will be summarized using frequency counts and percentages. Exact confidence intervals for point estimates may be provided. Statistical testing will be one-sided with a significance level of 0.025 or two-sided significance level of 0.05 unless specify otherwise. Data listings of individual subject data may be provided.

As described above, the primary analyses of the primary and secondary effectiveness endpoints will be based on the PP population, although the analyses will also be performed on the ITT population. The safety data will be summarized based on the ITT population.

### **11.4.1 PRIMARY EFFECTIVENESS ENDPOINT**

Proportion of eyes with a  $\geq 20\%$  decrease in unmedicated mean diurnal IOP at the 12-month postoperative examination compared to baseline will be calculated. The binomial distribution will be used to derive the exact 95% confidence interval of the percent. The

proportion will be compared against the performance goal of 0.4 (or 40%) based on binomial distribution.

[REDACTED]

For the analyses based on the ITT population, the following imputation for subjects with missing 12-month data but without SSI may be performed:

- The within-eye worst IOP (collected after 3 months postoperatively or IOP at baseline for the subjects with no data after postoperative 3 months) for the missing 12-month IOP and worst number of IOP lowering medications (collected after 3 months postoperatively or IOP-lowering medication data at baseline for the subjects with no data after postoperative 3 months) for the missing 12-month number of IOP-lowering medications.
- The worst IOP (collected after 3 months postoperatively or IOP at baseline for the subjects with no data after postoperative 3 months) during the study for the missing 12-month IOP and worst number of IOP-lowering medications (collected after 3 months postoperatively or IOP-lowering medication data at baseline for the subjects with no data after postoperative 3 months) during the study for the missing 12-month number of IOP-lowering medications.
- The mean IOP during the study for the missing 12-month IOP and mean number of IOP-lowering medications during the study for the missing 12-month number of IOP-lowering medications.
- The last-observed-carried-forward approach.

**11.4.2** [REDACTED]

[REDACTED]

[REDACTED]

[REDACTED]

- [REDACTED]

[REDACTED]

[REDACTED]

[REDACTED]

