## **9.4 SCREENING VISIT**

After obtaining an understanding of the purpose of this study, then reviewing and signing the Informed Consent Document, all potential subjects will undergo an initial screening examination in order to determine their eligibility for the study. Exams and tests listed in the Screening column of Table 1 should be performed. Refer to Appendix A for instructions for performing the exams.

If a subject does not meet the inclusion/exclusion criteria, he/she may be re-screened after 30 calendar days. Subject should be exited from the study and assigned another subject identification number at the second screening.

Exam data collected on subjects prior to enrollment as part of the routine clinical practice may serve as Screening data as long as it was collected within 15 days prior to the visit. The only exceptions to this are:

- IOP and IOP-lowering medications. These data must be collected at the Screening visit.
- Visual field: Visual Fields conducted per the protocol method (Humphrey 24-2 SITA standard) within 6 months of the screening visit will be acceptable.

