### **9.5 WASHOUT OF HYPOTENSIVE MEDICATIONS**

Subjects on ocular hypotensive medication who meet all eligibility criteria at the screening visit will be instructed to discontinue their ocular hypotensive medication regimen, and to return for a Baseline visit after completing the appropriate washout period. The final eligibility assessment will happen at baseline visit.

[REDACTED]

[REDACTED]

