### 11.4.3 COVARIATE ANALYSIS

The following variables will be examined for their prognostic value to the primary and secondary effectiveness endpoints using the PP population with the imputation used for the IOP-related SSIs:

- Age group (based on observed quartiles)
- Gender (male and female)
- Race (White and non-White)
- Ethnicity
- Baseline IOP group (based on observed quartiles)
- Screening Number of IOP-lowering medications (0, 1, 2, 3 and 4)  
*Note: the grouping of medication number may be changed based on the observed data.*
- Study site

For the primary effectiveness endpoint and the second secondary effectiveness endpoint, Fisher's test will be performed. For the first secondary effectiveness endpoint, one-way ANOVA with one of the factors listed above will be used to check the possible covariate effects. A p-value of 0.15 will be used for evaluating the possible covariate effects.

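### The worst-value ITT imputations in 11.4.1 take the fallback medication count from Baseline, which follows washout, so read literally they return the most favourable count (minor)

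*Combined protocol and SAP*

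**What the plan says.** Section 11.4.1 lists four imputations for the ITT analyses. Their status is permissive: "the following imputation for subjects with missing 12-month data but without SSI may be performed". The first two are worst-value rules, each with a fallback for subjects who have nothing recorded after month 3. For pressure the fallback is "IOP at baseline for the subjects with no data after postoperative 3 months". For the medication count it is "IOP-lowering medication data at baseline for the subjects with no data after postoperative 3 months". The first rule is stated to be within-eye. The second omits that qualifier and refers to the worst value during the study, but its fallback wording is the same. The other two (mean during the study, and last observation carried forward) have no baseline fallback.

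Section 9.5 fixes when Baseline happens. Subjects on drops are told to "discontinue their ocular hypotensive medication regimen, and to return for a Baseline visit after completing the appropriate washout period".

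Wherever else the readable text needs a medication reference, it uses Screening:

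- Section 9.4 does not accept earlier clinic records for these items: "IOP and IOP-lowering medications. These data must be collected at the Screening visit".
- Section 11.4.3 takes the number of medications from Screening as a covariate, with categories 0 to 4, and takes IOP from Baseline.
- Section 11.4.4 specifies that "the change in number of hypotensive medications from Screening to 12 Month (before washout if it is needed) will be calculated", while percent change in IOP runs from baseline.
- Section 11.6 refers the interim medication outcomes to the screening visit.

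**The concern.** The plan has two preoperative reference points for good reason. Unmedicated IOP can only be measured after washout, at Baseline; the usual drug regimen can only be counted before washout, at Screening. The fallback in 11.4.1 uses Baseline for both. For IOP that is conservative, since it gives a 0% change. For medications it gives a count of 0 to anyone whose drops were stopped for washout, so a subject who disappears early is recorded as having come off all treatment.

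A worst-value imputation exists to show that a result survives an unfavourable assumption about missing data. Here the medication half of the rule works the other way, and a larger number of early losses would make the medication result look better. Medication use is one of the two outcomes named in the study objective, and sections 11.2 and 11.4 commit to ITT analyses of the secondary endpoints as well as the primary one.

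**Working it through.** The plan states no figure on this point to reproduce. The sample size of 91 evaluable eyes does not enter the argument. The check is to apply the written rule to one subject and then to a mean.

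**One subject.** Take an eye on *m* medications at Screening, with no data after month 3 and no SSI.

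| Quantity | Fallback as written (within-eye rule) | Medication fallback from Screening |
|---|---|---|
| 12-month IOP | baseline IOP | baseline IOP |
| IOP decrease | 0%, below 20%: failure | 0%, below 20%: failure |
| 12-month medication count | 0 | *m* |
| Change from Screening | 0 − *m* = −*m* | *m* − *m* = 0 |

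With *m* = 3 the change is −3 as written and 0 with the Screening count. With *m* = 0 the two agree. For comparison, section 11.4.4 gives an eye with an SSI a medication change of 0 and an IOP change of 0%. The early dropout therefore gets the same IOP result as an SSI eye but a better medication result.

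**Mean change.** Let *e* be the share of analysed subjects with no data after month 3 and no SSI, *m* their mean Screening count, and *c* the mean change in everyone else.

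- As written: (1 − *e*)*c* − *e m*
- With the Screening count: (1 − *e*)*c*
- Difference in the device's favour: *e m*

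The readable text gives neither *e* nor *m*, so both are assumed here; *m* is limited by the 0 to 4 categories in 11.4.3.

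| *e* (assumed) | *m* = 1 | *m* = 2 | *m* = 3 | *m* = 4 |
|---|---|---|---|---|
| 2% | 0.02 | 0.04 | 0.06 | 0.08 |
| 5% | 0.05 | 0.10 | 0.15 | 0.20 |
| 10% | 0.10 | 0.20 | 0.30 | 0.40 |
| 15% | 0.15 | 0.30 | 0.45 | 0.60 |

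For example, with *c* = −1.0, *e* = 10% and *m* = 2: 0.9 × (−1.0) − 0.1 × 2 = −1.10 as written, against 0.9 × (−1.0) = −0.90 with the Screening count.

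**Proportion drug-free.** If the endpoint were instead the proportion on no drops at 12 months, the shift would be at most *e*, reached when every affected subject was on at least one drop at Screening. With 60% of the others drug-free and *e* = 10%: 0.9 × 0.6 + 0.1 = 64%, against 0.9 × 0.6 = 54%.

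**Which analyses could carry this.**

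- Primary endpoint, ITT: unchanged, because the IOP fallback makes the eye a failure whatever medication count is filled in.
- Medication change in 11.4.4: per-protocol. Section 11.2 requires 12-month IOP and medication data for that population, except for SSI eyes, so an early dropout without an SSI is not in it.
- Secondary endpoints, ITT: planned under 11.2 and 11.4, but their definitions and section 11.4.2 are redacted. Section 11.4.3 shows only that the first is examined by ANOVA and the second by Fisher's test.

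**The case against.** The strongest reply is that 'baseline' here loosely means the preoperative regimen. A worst-value rule whose fallback is always zero makes little sense, the text does not say 'Baseline visit', and the Baseline section (9.6), the rest of 9.5 and the visit schedule are not readable. That may well be the intention. But the readable text keeps the two visits apart and assigns medication counts to Screening, and a programmer working from 11.4.1 could reasonably pull the Baseline record. If Screening was meant, the correction only says so.

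A second reply concerns the second rule. If its worst value during the study means the worst across all subjects, an early dropout could be given the study maximum rather than 0. That reading is open, so the problem is certain only for the within-eye rule. The fallback phrase is nevertheless identical in both.

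Third, the imputations are optional, confined to the ITT population, and supportive of a per-protocol primary analysis; two of the four are not touched. All of this stands and limits the importance of the point.

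A reader might infer more than the documents support:

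- *That the primary result is biased.* It is not; the affected eye fails on IOP under either fill.
- *That the 12-month medication change in 11.4.4 is biased.* That analysis excludes these subjects.
- *That every early loss is credited with stopping all drops.* Subjects on 0 drops at Screening are unaffected, and those with an SSI fall outside the rule.

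**Conclusion.** The medication fallback is wrongly stated. For a subject on drops at Screening with no data after month 3 and no SSI, the within-eye rule read literally fills in 0, which contradicts both its worst-value purpose and the plan's own choice of Screening as the medication reference. The second rule has the same wording, subject to the ambiguity above.

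The reach is narrow: only ITT secondary analyses that use the 12-month medication count. Whether any exist cannot be seen, so the actual effect cannot be determined. If a mean change is analysed, the bias toward the device is *e m*. The 0.10 medications at 5% and 2 drops is an illustration on assumed inputs, not an estimate for this trial. The conclusion also rests on no unreadable text redefining baseline for medications. Severity: minor.

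**What to change.** In both worst-value rules of 11.4.1, replace the medication fallback with *number of IOP-lowering medications at the Screening visit (before washout)*, and leave the IOP fallback at baseline. In the same edit, state whether the second rule takes its worst value within the eye or across subjects.

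The cost is a wording change in two bullets. Section 9.4 already makes the Screening count mandatory, so no visit, data item or sample size changes. Any imputed ITT medication result becomes somewhat less favourable. The change should be made before the 12-month data are analysed, so that the reference visit is not chosen with results in view.
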